Appendix 4: EQ-5D

By placing a tick in one box in each group below, please indicate which statements best describe your own health state today.

**Mobility**

- I have no problems in walking about
- I have some problems in walking about
- I am confined to bed

**Self-Care**

- I have no problem with self-care
- I have some problems washing or dressing myself
- I am unable to wash or dress myself

**Usual activities (e.g. work, study, housework, family or leisure activities)**

- I have no problems with performing my usual activities
- I have some problems with performing my usual activities
- I am unable to perform my usual activities

**Pain/discomfort**

- I have no pain or discomfort
- I have moderate pain or discomfort
- I have extreme pain or discomfort

**Anxiety/depression**

- I am not anxious or depressed
- I am moderately anxious or depressed
- I am extremely anxious or depressed

To help people say how good or bad a health state is, we have drawn a scale (rather like a thermometer) on which the best state you can imagine is marked 100 and the worst state you can imagine is marked 0.

We would like you to indicate on this scale how good or bad your own health is today, in your opinion. Please do this by drawing a line from the box below to whichever point on the scale indicates how good or bad your health state is today.

how good or bad  
your own health is today

**Questionnaire completed by:**

- 1 Patients independently
- 2 Patients with help of others
- 3 Agent (the patient's family members)

Appendix 5: Abnormal clinical laboratory indicators

bleeding tendency	Prothrombin time >1.5 times control or platelet count <10×10  /L
moderate or severe anemia	Hemoglobin (Hb) <90g/L
abnormal liver function	Transaminase beyond the normal more than two times
Abnormal renal function	Serum creatinine >1.5mg/dl or creatinine clearance rate <50ml/min

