##### 4.6.3.2 Adverse Event Collection

No specific laboratory safety tests are required during this study. However, if a laboratory abnormality is clinically relevant or leads to an adverse event report, specific appropriate actions may be required (see Appendix 5, decision charts).

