#### Exclusion Criteria

- Diagnosis of hemorrhage or other pathology, such as vascular malformation, tumor, abscess or other major non-ischemic brain disease (e.g., multiple sclerosis) on baseline head CT or MRI.
- Isolated or pure sensory symptoms (e.g., numbness), isolated visual changes, or isolated dizziness/vertigo without evidence of acute infarction on baseline head CT or MRI.
- Modified Rankin Scale Score  $> 2$  at randomization (pre-morbid historical assessment)
- NIH Stroke Score  $\geq 4$  at randomization
- Clear indication for anticoagulation (presumed cardiac source of embolus, e.g., atrial fibrillation, prosthetic cardiac valves known or suspected endocarditis).
- Contraindication to clopidogrel or ASA.
  - Known allergy
  - Severe renal or hepatic insufficiency
  - Severe cardiac failure, asthma
  - Hemostatic disorder or systemic bleeding
  - History of hemostatic disorder or systemic bleeding
  - History of thrombocytopenia or neutropenia
  - History of drug-induced hematologic or hepatic abnormalities
  - Low white blood cell ( $<2 \times 10^9/l$ ) or platelet count ( $<100 \times 10^9/l$ ).

- Use of thrombolysis within 24 hours prior to randomization
- History of intracranial hemorrhage.
- Anticipated requirement for long-term non-study antiplatelet drugs, or NSAIDs affecting platelet function.
- Current treatment (last dose given within 10 days before randomization) with heparin therapy or oral anti coagulation.
- Gastrointestinal bleed or major surgery within 3 months.
- Planned or likely revascularization (any angioplasty or vascular surgery) within the next 3 months (if clinically indicated, vascular imaging should be performed prior to randomization whenever possible)
- Scheduled for surgery or interventional treatment requiring study drug cessation.
- Qualifying TIA or minor stroke induced by angiography or surgery.
- Severe non-cardiovascular comorbidity with life expectancy < 3 months.
- Women of childbearing age not practicing reliable contraception who do not have a documented negative pregnancy test.
- Currently receiving an investigational drug or device.

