##### **7.5.1 Temporary treatment discontinuation with investigational product(s)**

Re-initiation of treatment with the Investigational Product will be done under close and appropriate clinical/and or laboratory monitoring (see Appendix 5 Decision Charts) once the Investigator has considered according to his/her best medical judgment that the role of the

Investigational Product(s) in the occurrence of the event concerned was unlikely and there is no other contraindication to continuing in the study.

All temporary treatment discontinuation (< 10 days) and the date of treatment re-initiation should be recorded by the Investigator on the appropriate CRF pages when considered to be confirmed

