### **7.5.2 Definition treatment discontinuation with investigational product(s)**

A patient should discontinue the study drug for any of the following reasons:

- ✓ Intercurrent condition that requires discontinuation of the study (e.g. lab abnormalities, Appendix 5).
- ✓ Positive serum pregnancy test or desire to become pregnant
- ✓ Contraception cessation

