## **8.2 Definitions of Adverse Event (AE) and Serious Adverse Event (SAE)**

An **Adverse Event** is any untoward medical occurrence in a patient or clinical investigation patient administered a pharmaceutical product and which does not necessarily have to have a causal relationship with this treatment.

Efficacy endpoints will not be considered as AEs except if, because of the course or severity or any other features of such events, the Investigator, according to his/her best medical judgment, considers these events as exceptional in this medical condition.

A **Serious Adverse Event** is any untoward medical occurrence that at any dose:

- ✓ Results in death, or
- ✓ Is life-threatening, or

Note: The term "life-threatening" in the definition of "serious" refers to an event in which the patient was at risk of death at the time of the event; it does not refer to an event which hypothetically might have caused death if it were more severe.

- ✓ Requires inpatient hospitalization or prolongation of existing hospitalization, or
- ✓ Results in persistent or significant disability/incapacity, or
- ✓ Is a congenital anomaly/birth defect, or
- ✓ Is a medically important event

Medical and scientific judgment should be exercised in deciding whether expedited reporting is appropriate in other situations, such as important medical events that may not be immediately life-threatening or result in death or hospitalization but may jeopardize the patient or may require intervention to prevent one of the other outcomes listed in the definition above.

These should also usually be considered serious.

Note: Examples of such events are intensive treatment in an emergency room or at home for allergic bronchospasm, blood dyscrasias, convulsions or asymptomatic ALT increase  $\geq 10$  ULN that does not result in hospitalization, or development of drug dependency or drug abuse.

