### **8.3 Obligation of the investigator regarding safety reporting**

#### **8.3.1 Adverse Events**

All Adverse Events regardless of seriousness or relationship to Investigational Product, spanning the time from the first visit planned in the Clinical Trial Protocol/signature of the informed consent (i.e., occurring during the washout period) to the last visit planned in the protocol, are to be recorded on the corresponding page(s) included in the Case Report Form. Whenever possible, symptoms should be grouped as a single syndrome or diagnosis. The Investigator should specify the date of onset, intensity, action taken with respect to Investigational Product, corrective treatment/therapy given, outcome and his/her opinion as to whether there is a reasonable possibility that the Adverse Event was caused by the Investigational Product.

Laboratory, vital signs or ECG abnormalities are to be recorded as Adverse Events only if they are medically relevant: symptomatic, requiring corrective treatment, leading to discontinuation and/or fulfilling a seriousness criterion.

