**附表 5: 临床重要的实验室指标异常**

出血倾向	凝血酶原时间超过对照 1.5 倍或血小板计数 $<10 \times 10^9/L$
中、重度贫血	血红蛋白 (Hb) $<90g/L$
肝功能异常	转氨酶超过正常 2 倍以上
肾功能异常	血肌酐 $>1.5mg/dl$ 或肌酐清除率 $<50ml/min$

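### The Appendix 5 platelet limit that sites consult for stopping and acting on laboratory results is <10×10⁹/L, one tenth of the count the exclusion criteria treat as a contraindication to the same drugs

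*Supplement*

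**What the plan says.** Appendix 5 of the final English protocol is a four-row table of laboratory limits. Its only platelet figure is in the bleeding-tendency row: "Prothrombin time >1.5 times control or platelet count <10×10" (×10⁹/L). The Chinese final protocol prints the same limit: "凝血酶原时间超过对照 1.5 倍或血小板计数 $<10 \times 10^9/L".

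Three places in the body of the protocol send the reader to that table:

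- Section 7.5.2, definitive discontinuation, lists as a reason "Intercurrent condition that requires discontinuation of the study (e.g. lab abnormalities, Appendix 5".
- Section 4.6.3.2 says that for a clinically relevant laboratory abnormality "specific appropriate actions may be required (see Appendix 5, decision charts". The SAP repeats the reference under its safety endpoints.
- Section 7.5.1, on restarting after a temporary stop, asks for clinical and/or "laboratory monitoring (see Appendix 5 Decision Charts".

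The exclusion criteria use a different platelet figure. Under contraindications to clopidogrel or ASA they list "Low white blood cell ( $<2 \times 10^9/l$ ) or platelet count ( $<100 \times 10^9/l". The synopsis and the Chinese exclusion criteria agree.

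**The concern.** Bleeding is the main expected harm of the regimen and its primary safety endpoint (section 4.6.3.4), and thrombotic thrombocytopenic purpura is a named safety outcome (section 3.2.5). A site that finds a low platelet count on treatment, and looks up the table that section 7.5.2 points to, meets a limit one tenth of the one the protocol uses at the door. A count of 20×10⁹/L, for example, would have kept the patient out of the trial but matches no platelet line in Appendix 5.

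At stake is the quality of one safety reference. A printed limit that low may reassure a site about a count that the protocol elsewhere regards as incompatible with either drug.

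**Working it through.** No sample-size or error-rate formula applies. The check compares two printed limits in the same unit and then asks what the citing sections do with the lower one.

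**Inputs**

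| Item | Limit | Where |
|---|---|---|
| On-study platelet abnormality | <10×10⁹/L | Appendix 5, final English and final Chinese |
| Entry contraindication | <100×10⁹/L | Exclusion criteria in section 5 and synopsis, final English and final Chinese |

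**Size of the gap**

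- Ratio of the limits: 100 / 10 = 10.
- Counts that bar entry but match no platelet line in Appendix 5: at least 10 and below 100×10⁹/L.
- Fall from the lowest eligible count to the Appendix 5 limit: (100 − 10) / 100 = 90%. A patient who enters at 100×10⁹/L must lose more than 90% of platelets before the line is met.

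**Is the figure a reading error?** Probably not. The same value appears in version 1.0 of the protocol, in the final English text and in the final Chinese text. None of the listed protocol amendments touches it.

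**Does it fit the rest of the table?** The other limits mark moderate abnormality: prothrombin time above 1.5 times control, haemoglobin below 90 g/L, transaminase more than twice normal, creatinine above 1.5 mg/dl. The transaminase line can be compared with an entry rule. The exclusion criteria in the Chinese synopsis define severe hepatic insufficiency as ALT or AST above twice the upper limit of normal, so there the Appendix 5 limit and the entry limit agree. The platelet line is the one far out of step.

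**What does each citing section do with the table?**

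- *Stopping (7.5.2).* Appendix 5 is the only laboratory example given. A count between the two limits is not among the listed abnormalities.
- *Action on abnormalities (4.6.3.2).* The same gap arises, although action is discretionary.
- *Restart (7.5.1).* The section allows restart only if the investigator thinks the drug unlikely to have caused the event and nothing else contraindicates continuing. Read with the exclusion criteria, a count below 100×10⁹/L already stands in the way of restart, so the gap does little here.

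**How often would it arise?** Section 4.6.3.2 requires no specific safety laboratory tests during the study. The schedule in section 1.2 places laboratory tests, with platelets included, at screening and at the event visit. The event-visit procedures in section 9.4 do not list a blood count. On-treatment counts would therefore come mainly from event visits or clinical suspicion. The documents give no basis for estimating the number of patients.

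**The case against.** The strongest reply is that Appendix 5 is not a stopping rule. It contains no instruction to stop, hold or continue, and section 7.5.2 cites it only by way of example. Section 4.6.3.2 leaves action to the circumstances. Other safeguards are in place: section 8.2 gives as serious-event examples "allergic bronchospasm, blood dyscrasias, convulsions or asymptomatic ALT increase", and under section 8.3.1 "Laboratory, vital signs or ECG abnormalities are to be recorded as Adverse Events only if they are medically relevant", so clinically important thrombocytopenia would still be reported. All of this stands, and it keeps the point small. It does not explain why a table offered to guide judgment should carry a limit so far below the protocol's own contraindication.

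A second reply is that an on-treatment limit may properly be laxer than an entry limit. That is true in general. Here the gap is tenfold, no reason is given, and the one other line that can be compared directly is no laxer than its entry counterpart.

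A third reply concerns the remedy. Under section 7.5.2, a bare <100×10⁹/L would turn a count of 99 in a patient who entered at 100 into an example of a reason for definitive stopping. Section 7.5 calls for study drug to be continued where possible and treats permanent discontinuation as the final option. This objection is right, and the fix has to respect it.

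A reader might also infer that the protocol tells sites to continue treatment at 10 to 99×10⁹/L, or that it permits restart at such counts. The documents support neither: no text calls those counts acceptable, and section 7.5.1 already restricts restart.

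**Conclusion.** The point holds as a minor safety correction. The table that the protocol cites for laboratory reasons to stop study drug has a platelet limit one tenth of its own contraindication level, and on-treatment counts from 10 up to, but not including, 100×10⁹/L match no platelet line in it. Restart is already limited by section 7.5.1, and investigator judgment and adverse-event reporting apply throughout.

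The figure looks like a dropped zero, and a reader might conclude that it is one. The documents do not confirm this, and the point does not depend on it: intended or not, the gap is unexplained. The conclusion assumes that sites use Appendix 5 as the citing sections direct. Power, alpha and the primary analysis are unaffected.

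**What to change.** In Appendix 5, change the platelet limit from <10×10⁹/L to <100×10⁹/L in both the English and the Chinese protocol. State beside it that a count below this level is the trigger to hold study drug and review the patient, as a temporary discontinuation under section 7.5.1. Leave definitive discontinuation to the investigator's judgment under section 7.5.2, so that a count just under the limit does not by itself point to permanent stopping. Tell sites by memo. If the sponsor prefers another on-treatment limit, it should print that limit and give the reason.

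The cost is one figure and a short note in two languages, plus the memo. No new tests are needed, since platelets already belong to the laboratory panel scheduled at screening and at event visits. The downside is a few more temporary drug interruptions for thrombocytopenia.

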Appendix 6: GUSTO classification

Severe Bleeding	Documented intracranial hemorrhage or bleeding that causes hemodynamic compromise requiring blood or fluid replacement, inotropic support, ventricular assist devices, surgical intervention (other than vascular site repair), or CPR to maintain a sufficient cardiac output.
Moderate Bleeding	Bleeding that requires transfusion of blood but does not lead to hemodynamic compromise requiring intervention.
Mild Bleeding	Bleeding not requiring transfusion and not causing hemodynamic compromise. This includes subcutaneous bleeding, mild hematomas, oozing from puncture sites, etc.

## **Summary of protocol amendments**

### **APPENDIX I :**

#### **Protocol changes version 1.0 (Jan 03, 2009) to 1.1 (Feb. 25, 2009)**

- ✧ Dose regimen (page 33): For Group 1, duration of combination of aspirin 75 mg/day is changed from first 30 ( $\pm 7$ ) days into first 21( $\pm 2$ ) days.
- ✧ Study procedures (page 43): hospital discharge is deleted and Day 30 Visit is changed into Day 21 Visit.

### **APPENDIX II :**

#### **Protocol changes version 1.1 (Feb. 25, 2009) to 1.2 (Mar. 15, 2009)**

- ✧ 10.1.1 Sample Size Estimates (10.1.1.1 Primary Null Hypothesis, page 47; 10.1.1.1.6 Power and alpha, page 52): 80% statistical power to detect a relative risk reduction of 22% is changed into 90% power. Therefore, sample size of 3800 will be replaced by 5100.

### **APPENDIX III:**

#### **Protocol changes version 1.2 (Mar. 15, 2009) to 1.3 (May 20, 2009)**

- ✧ Study objectives (3.2 Secondary, page 22): two subgroups are added.
  - 3.2.11. To compare efficacy and safety by time to randomization,  $< 12$  hours vs.  $\geq 12$  hours.
  - 3.2.12. To evaluate the primary outcome and intracranial hemorrhage in those with and without imaging evidence of infarction on the initial head CT or MRI imaging.
- ✧ Number of Centers: Up to about 80 investigational sites in the China in Clinical Research Network is change into about 100 sites.

- ✧ 7.4.2 Permitted Concurrent Treatments (page 37): proton-pump inhibitors are avoided with consideration for between omeprazole and other proton pump inhibitors and clopidogrel. So, the following content is added:

Given uncertainty about an interaction between omeprazole and other proton pump inhibitors and clopidogrel, those previously taking a proton-pump inhibitor will be evaluated for the appropriateness of other agents, such as H2 blockers. New prescriptions for proton-pump inhibitors will be avoided whenever an H2 blocker or other agent is an acceptable option. Similarly, other drugs that theoretically may affect clopidogrel metabolism will be avoided, with others substituted. This list includes: esomeprazole (Nexium), cimetidine (which is available by prescription Tagamet and OTC as Tagamet HB), fluconazole (Diflucan), ketoconazole (Nizoral), voriconazole (VFEND), etravirine (Intelence), felbamate (Felbatol), fluoxetine (Prozac, Serafem, Symbyax), and fluvoxamine (Luvox).

## Introduction

This statistical analysis plan (SAP) documents the planned statistical analyses for the CHANCE study and is based on the protocol, together with any subsequent amendments.

This SAP is intended for the use of project team members within Beijing Tiantan Hospital, and should be read in conjunction with the aforementioned protocol.

## Study Objective(s) and Endpoint(s)

### Study Objective(s)

The primary objective of this study is to assess the effects of a 3-month regimen of clopidogrel initiated with a loading dose of 300 mg followed by 75 mg/day combined with aspirin 75 mg/day during the first 30 Days versus a 3-month regimen of aspirin 75 mg/day alone on reducing the 3-month risk of any new stroke (ischemic or hemorrhagic) when initiated within 24 hours of symptom onset in high-risk patients with TIA or minor stroke.

The secondary objectives of this study are:

- To assess the secondary composite outcome: composite of any stroke, myocardial infarction, and vascular death
- To assess separately the effects of this Clopidogrel regimen versus ASA alone on the incidence of: new clinical vascular events (ischemic stroke/ hemorrhagic stroke/ TIA/ MI/ vascular death) as a cluster and evaluated individually.
- To assess whether there are differential treatment effects in predefined subgroups:
  - ✧ (<65 years vs ≥65 years)
  - ✧ Sex (male vs female)
  - ✧ Index event (minor stroke vs TIA)
  - ✧ TIA risk stratification ( $ABCD^2=4$  vs  $ABCD^2>4$ )
  - ✧ Previous stroke
  - ✧ Previous TIA
  - ✧ History of hypertension
  - ✧ History of diabetes
  - ✧ Systolic blood pressure at baseline (<140mmHg vs ≥140mmHg)
  - ✧ Aspirin taken within 24h
- To assess the primary outcome measure in a Per-protocol (PP) population. This will include all patients who have not had a significant interruption of study drug (Actual number doses taken less than 80% of expected number of doses taken) or major protocol violation.

Other objectives are:

- To evaluate treatment differences if changes in modified Rankin Scale from baseline to the last follow-up.
- To compare the safety of the two treatment regimens in terms of:
  - ✧ Severe or moderate bleeding (GUSTO definition)
  - ✧ Intracranial hemorrhage
  - ✧ Total mortality
  - ✧ AEs/SAEs

- In further exploratory analysis, to evaluate treatment differences of impairment (change in NIHSS scores), and Quality of Life (EuroQol EQ-5D scale) among survivors.

### Study Endpoint(s)

#### **Primary Efficacy**

- Rate of new stroke (both ischemic and hemorrhagic) reported during the 3-month treatment period.

#### **Secondary Efficacy**

- Rate of the composite outcome: including any stroke, myocardial infarction, and vascular death as a cluster and evaluated individually

#### **Other Efficacy**

- Changes of the Modified Rankin Scale scores between the end of study and baseline.
- Further efficacy exploratory analysis:
  - ✧ Changes in NIHSS scores between the end of study and baseline.
  - ✧ Changes in EuroQol EQ-5D scale between the end of study and baseline.

#### **Safety Endpoint**

- Rate of moderate and severe bleeding incidence (GUSTO definition), including fatal bleeding and symptomatic intracranial hemorrhage
- Rate of symptomatic and asymptomatic intracranial hemorrhagic events at 3 months
- Rate of total mortality
- Incidence of AEs/SAEs (as described in the protocol) reported by the investigators

Clinical safety will be assessed by a physical examination including neurological evaluation at D1, hospital discharge, M1 and M3 visits. Adverse events will be collected at each visit after baseline. Supine blood pressure and heart rate will be measured at each visit. No specific laboratory safety tests are required during this study. However, if a laboratory abnormality is clinically relevant or leads to an adverse event report, specific appropriate actions may be required (see Appendix 5, decision charts). An ECG will be performed at the baseline visit (Day 1).

### Statistical Hypotheses

The primary endpoint for this study will be the rate of new stroke (both ischemic and hemorrhagic) reported during the 3-month treatment period.

The null hypothesis of no difference in this rate between the two treatment groups will be tested using a two-sided test at the 5% level of significance

$$H_0: \lambda_1/\lambda_2 = 1$$

$$H_1: \lambda_1/\lambda_2 \neq 1$$

Where  $\lambda_1$  is the rate of new stroke over the 3-month treatment period in the group treated with Clopidogrel/ASA regimen and  $\lambda_2$  is the same endpoint in the group treated with ASA alone.

